2 STUDY OBJECTIVES

2.1 Primary Objectives

Determine feasibility of using tumor samples to assess genomic sequencing using predictive modeling to make real-time treatment decisions for children with relapsed/refractory cancers.

2.2 Secondary Objectives

- ◆ To determine the activity of treatments chosen based on:
 - Overall response rate (ORR)
 - Progression free survival (PFS)
- ◆ To continue to evaluate the safety of allowing a molecular tumor board to determine individualized treatment plans
- ◆ (Voluntary) To explore the relationship between tumor phenotype/genotype and response by permitting use of tumor tissue in a correlative biologic study
- ◆ To compare PFS interval to PFS intervals of previous chemotherapy regimens since relapse for each subject.
- ◆ Sub analysis examination of disease types.

2.3 Subject Enrollment and Sample Procurement and Data Processing

Eligible subjects will be enrolled onto this study at each site following a registration process that includes receipt of a signed subject consent form and a copy of the required baseline laboratory tests. Subjects will undergo a scheduled surgical resection and/or diagnostic biopsy procedure.

Common sample identifiers will be provided by the NMTRC Lead Study Coordinator to the participating site and will be used by all parties throughout the project to ensure sample, data and report alignment between participating organizations. At the time of tissue resection or biopsy, fresh tumor samples and a blood sample will be committed for this specific research study (referred to as “Primary Samples”), and prepared immediately per Appendix II and section 9.3. Primary Samples will be sent to Ashion Analytics, LLC, which is a CLIA-certified laboratory housed at the Translational Genomics Reserach Institute (TGen). Samples will be reviewed by local pathology to confirm that the sample sent to TGen contains >50% tumor cell viability which is the minimum required for successful analysis. The absence of an adequate tumor specimen from an enrolled subject will make them not eligible to continue on the study. Tumor

samples will also be sent for research purposes (referred to as “Secondary Samples.”) A portion of the tumor tissue biopsy will be shipped overnight to the [name] Pediatric Oncology Translational Research Laboratory on dry ice.

Upon arrival of the tumor specimens at Ashion and the [name] Pediatric Oncology Translational Research Laboratory, the samples will be logged and immediately processed according to details in Section 9.

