ESTIMATED NUMBER OF PATIENTS/GEOGRAPHIC REGIONS	
200 evaluable (220 total) relapsed/refractory pediatric cancer patients. Additional patients may enroll through compassionate access if no other treatment options are available.
 
Patients will enroll at:
 
Arnold Palmer Children's Hospital, FL St. Louis University/Cardinal Glennon Children's Medical Center, MO Helen DeVos Children's Hospital, MI Levine Children's Hospital, NC Connecticut Children's Medical Center, CT Children's Mercy Hospital, Kansas City MO Rady Children's Hospital of San Diego, CA Medical University of South Carolina, SC Monroe Carrell Jr. Children's Hospital at Vanderbilt, TN Kapiolani Medical Center for Women and Children, HI Dell Children's Hospital, TX Texas Children's Hospital, Baylor College of Medicine, TX Primary Children's Hospital, UT Children's Hospital and Clinics of Minnesota, MN Penn State Milton S. Hershey Medical Center and Children's Hospital, Hershey, PA Arkansas Children's Hospital – Little Rock, AR 
International Sites
 American University of Beirut Medical Center, Lebanon La Timone; Marseille, France

LENGTH OF STUDY	Accrual to this study is estimated to be approximately 3-4 years.
STUDY ASSESSMENTS	Refer to Table of Assessments for timing of study procedures.
CRITERIA FOR EVALUATION	
Feasibility Measures: Primary objective: The definition of feasibility for this study will include: “Enrollment onto study, genomic profile, analysis and report generation completed, tumor board held with treatment decision, treatment review completed, start of treatment, and completion of 1 cycle of therapy.”
 
Efficacy Measures: Secondary objectives Response: To determine the overall response rate (ORR) by the presence of radiologically assessable disease by cross-sectional CT or MRI imaging and/or by MIBG or PET scans.
 
 ◆ Duration of response, defined as the period of time from when measurement criteria are met for complete response (CR) or partial response (PR), whichever is first recorded, until the first date that recurrent or progressive disease (PD) is objectively documented (taking as reference for PD the smallest measurements recorded since the treatment started) ◆ The assessment of response will include the initial measurable

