The primary objective of this feasibility study was to evaluate the feasibility and safety of using predictive modeling based on genome-wide mRNA expression profiles of neuroblastoma tumor biopsies to make real-time treatment decisions. Feasibility was defined as “enrollment onto study, quality mRNA obtained, gene chip completed, tumor board held, medical monitor review and approval, start of treatment by 21 days post biopsy/surgical resection date, and completion of 1 cycle of therapy.” Sixteen (16) subjects were enrolled to this study, all with multiply relapsed or refractory neuroblastoma. Subjects were between 1-11 years post diagnosis. All subjects had soft tissue disease which was able to be biopsied. All biopsies were adequate by pathology evaluation (>75% viable tumor) and RNA quality (>6.5 RIN). 2 subjects were deemed ineligible due to tumor type after biopsy. Gene chips were completed in 3-8 days (95% CI: 3.8 – 6.8), report generation took 0-3 days (95% CI: 0.0 – 1.5), tumor board took 1-6 days (95% CI: 1.6 – 4.2), medical monitor sign off took 1-2 days (95% CI: 0.8 – 1.4). The total time from date of biopsy to tumor board was 6-11 days (95% CI: 7.5 – 10.2) for all subjects and 7-20 days to treatment (95% CI: 8.9 – 16.1), with an average of 12.4 days. The tumor board which consisted of 4-15 pediatric oncologists from sites across the US and a pediatric oncology pharmacist was able to create individualized therapy regimens for all subjects. Correlative biology specimens were obtained and grown in culture. Mice xenograft establishment is ongoing. Cultures and xenografts are able to be used for validation studies of predicted drug sensitivity. Triplicate biopsies showed reproducible sets of drugs and the comparatively large differences in drug lists between patients show that the drug lists are tailored to patients. Comparison of RNA expression profiles with RNA sequencing from each patient showed strong correlation.

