The study endpoint showed that 14/14 patients were feasible to enroll, biopsy, genomic analysis, tumor board review and patient treatment was met. All regimens were found to be safe by the medical monitor proving that the molecular tumor board was able to make safe decisions similar to hospital tumor boards making treatment decisions without molecular information on the patients. It was felt that the pharmacy review for evaluating drug-drug interactions and deciding on laboratory and safety testing was an important part of the tumor board (this is not usually present at hospital tumor boards) and will continue to be incorporated in this and future trials. All patients tolerated therapy well and were treated without any serious adverse events related to study drugs. Clinical benefit was seen 64% of patients. This study shows that it is feasible to create therapeutic treatment plans based on genomic profiling in real time and that patients are able to be treated safely on a tumor board derived molecular guided therapy using existing medications

In this study we proposed to study reproducibility by applying it to triplicate samples obtained by dissecting each of five solid tumors. The primary goal of the reproducibility study is to evaluate the variation among sets of drug therapies associated with the same tumor. Secondary goals are 1) to compare the variation among sets of drug therapies from the same tumor with variation

between tumors from distinct patients and 2) to evaluate variation associated with earlier steps in the process, in particular, expression profiles and comparative expression profiles.

Distance-based nonparametric multivariate analysis of variance [41, 42] allowed us to reject the null hypothesis that variation between biopsies can be accounted for by the variation within biopsies ($p=0.001$). That the variation among expression profiles associated with the same biopsy is small compared with the variation between expression profiles associated with different biopsies is apparent from Principal Component Analysis (Figure 1).

Sets of drug therapies

Similarly, the variation among drug sets associated with the same biopsy is small compared with the variation among drug lists associated with different biopsies ($p=0.001$). The reproducibility averaged over patients, replicates, and drugs is 0.68. As the threshold score increases the reproducibility increases to 1 (Figure 2).

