- x. Ethesioneuroblastoma (At relapse after standard of care therapy and/or non- responsive/progressive to accepted curative chemotherapy).
- xi. Neuroendocrine tumors (At relapse after standard of care therapy and/or non- responsive/progressive to accepted curative chemotherapy).
- xii. Desmoplastic small round cell tumor (At relapse after standard of care therapy and/or non- responsive/progressive to accepted curative chemotherapy).
- xiii. Melanoma (At relapse after standard of care therapy and/or non- responsive/progressive to accepted curative chemotherapy).

2. Subjects must be age \geq 12 months at enrollment
3. Subjects must be age \leq 21 years at initial diagnosis
4. Subjects must have measurable disease as defined by RESIST v1.1 at the time of biopsy and tumor must be accessible for biopsy. Tumor samples submitted for analysis must contain $>50\%$ viable tumor tissue to qualify. In addition, subjects with disease confined to the bone marrow are eligible to enroll if the degree of marrow involvement is expected to be $>50\%$.
Note: Subjects who are expected to have no evidence of disease after surgical removal of their tumor are still eligible for this trial if their disease would normally require adjuvant chemotherapy treatment after surgery despite NED status.
5. Current disease state must be one for which there is currently no known effective therapy
6. Specimens will be obtained only in a non-significant risk manner and not solely for the purpose of investigational testing.
7. Lansky or Karnofsky Score must be ≥ 50
8. Subjects without bone marrow metastases must have an ANC $> 750/\mu\text{l}$ to begin treatment.
9. Subjects with CNS disease currently taking steroids must have been on a stable dose of steroids for 2 weeks prior to their biopsy and must not have progressive hydrocephalus at enrollment.
10. Adequate liver function must be demonstrated, defined as:
 - a. Total bilirubin $\leq 1.5 \times$ upper limit of normal (ULN) for age AND
 - b. ALT (SGPT) $< 10 \times$ upper limit of normal (ULN) for age
11. A negative serum pregnancy test is required for female participants of child bearing potential (≥ 13 years of age or after onset of menses)

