The assessment of response will include the initial measurable targets and will be performed after the second cycle, then after every other cycle (or 8 weeks, whichever occurs first). Serial results of bone marrow aspirates, biopsies and urinary catecholamines will be reviewed for responding subjects to confirm response or lack of progression.

Clinical Response

A subject will be defined as having a clinical response if they have stable disease or better and a decrease in their tumor markers by $\geq 50\%$. Clinical response will also be defined as a subject that has a complete clearing of a previously positive bone marrow while on study.

Progression Free Survival

Time to progression, defined as the period from the first day of administration of study drug until the criteria for progression are met taking as reference the screening measurements, will be assessed.

8 Sample Size Justification

Feasibility

Since this is primarily a feasibility trial, the definition of feasibility for this study will include:

“Enrollment onto study, genomic profile, analysis and report generation completed, tumor board held with treatment decision, treatment review completed, start of treatment, and completion of 1 cycle of therapy.”

Our preliminary results for 5 subjects indicates that we have a sample collection success rate of 5/5 (100%) subjects, a genetic report profile success rate of 5/5 (100%) within the 7-10 day time window as well as a treatment agreement success rate of 5/5 (100%) within the 5 day time window. The average time (+/-SD) for completion of the genetic profile was 6.6 days (+/-1.7 days) with a median of 7 days. The average time (+/-SD) for time to Treatment was 3.2 days (+/-0.8 days) with a median of 3 days. Data preliminary to date for each of these three feasibility markers are very consistent with our anticipated performance standards.

Our initial feasibility trial continues to show that it is feasible and safe to use RNA expression analysis and a DNA mutation panel for tumor boards creating treatment decisions for patients without curative options. This study will ask the feasibility of utilizing DNA exomes and RNA sequencing in a tumor for molecular guided therapy.

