The “Primary Sample” will be a current solid tumor biopsy or core bone marrow biopsy (with >50% viable tumor) along with a 4-6 mL blood sample collected in an EDTA tube.

If a solid tumor sample cannot be obtained and the subject’s bone marrow is <50% tumor then they will be ineligible for study.

In addition to the “Primary Sample”, if subjects have signed the additional consent for optional sample collection, they will also have these secondary samples sent as follows.

9.3.1 Sample Procurement and Shipping at Screening:

De-identified subject tumor samples will be sent on all subjects as following:

Label all tubes with subject’s unique identifier, date/time of sample collection, and contents (i.e. solid tumor, bone marrow, blood).

9.3.1.1 Send the following Required Primary Samples for All Tumor Types (along with appropriate form)

1. Required- Sample 1 (tumor)

Solid Tumor or Bone Marrow Core Biopsy (if solid tumor is not available)-
You will be provided a kit for tumor collection. This kit will include instructions, collection tubes and shipping instructions.

For sample 1 follow collection instructions in Appendix II (flash freeze tumor sample within 20 minutes of harvest, or sooner when possible) and ship overnight on at least 1kg of dry ice to:

*Note: Do NOT place sample in aluminum/tin foil at any time.

Ashion Analytics, LLC
[name]
[name]
[contact]
Lab [contact]
email: [contact]

For Biopsies- refer to Instructions for Core/Needle Biopsy Specimens for sample size instructions.

For Surgical resections- size of sample should be about the size of a pencil eraser. Minimum amount of tumor sample required is 50-200 mg of tissue.

2. Required- Sample 2 (blood):

Send 4-6 mL of blood in EDTA tube (ambient – prefer to have shipped on frozen gel pack in summer months May to October) to:

Ashion Analytics, LLC
[name]
[name]
[contact]
Lab [contact]
email: [contact]

9.3.1.2 Send the following Recommended secondary tumor samples along with appropriate forms listed in order of priority (please work your way down the list of tumor samples until you either run out of available sample or have completed all samples. Once this occurs move on to Bone Marrow samples):

You will be provided a kit for tumor collection (fresh snap frozen and in culture media). Follow collection instructions and ship as directed overnight.

3. Sample 3:

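### The plan makes an inadequate specimen an eligibility matter and never fixes the feasibility denominator, so the primary feasibility rate can be biased upward

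*Combined protocol and SAP*

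**What the plan says.** **The specimen as an eligibility matter.** Section 2.3 describes subjects who are enrolled, undergo biopsy or resection, and have the sample checked by local pathology for more than 50% viable tumor. It then states: "The absence of an adequate tumor specimen from an enrolled subject will make them not eligible to continue on the study". Inclusion criterion 4 (section 4.1) sets the same threshold as an entry condition: "Tumor samples submitted for analysis must contain" more than 50% "viable tumor tissue to qualify". For a subject with no solid tumor sample, section 9.3 says that if the "bone marrow is <50% tumor then they will be ineligible for study".

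**The endpoint.** The Synopsis and section 8 define feasibility as a chain. It starts at enrollment, includes "genomic profile, analysis and report generation completed", and ends with one completed cycle. Specimen adequacy is not a named link.

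**The counts.** The Synopsis gives "200 evaluable (220 total) relapsed/refractory pediatric cancer patients" and says that the 200 evaluable subjects will be treated. Section 8 adds subjects after Amendment 3.0, partly to gain further feasibility information on the new report, up to 200 evaluable. The protocol does not define evaluable.

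**The analysis.** Section 12.3 bases the success rate on 16 patients per stratum, without saying whether these are enrolled, eligible, treated or evaluable. Process failures appear there only as possible censored observations in Kaplan-Meier plots.

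**The concern.** Whether a usable specimen can be obtained is part of what this trial tests. Section 8 lists sample collection success first among its three preliminary feasibility markers, and section 2.3 calls the 50% threshold the minimum for successful analysis. The two earlier neuroblastoma trials in section 1.2 put RNA quality inside their feasibility definitions. In this protocol the specimen requirement sits in the eligibility rules.

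A child whose biopsy proves inadequate therefore has no assigned place in the primary result. Two analysts following the protocol could report different feasibility rates from the same records. One would count the child as a failure. The other would leave the child out as ineligible or not evaluable. The second choice can only raise the rate, and it lets the 50%-versus-75% rule pass more often than its stated error level. Section 8 already declares feasibility met in all strata at Amendment 3.0 without giving numerators or denominators, so the reader cannot tell which choice was made.

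**Working it through.** **1. Reproduce the design.** Inputs from section 8: null rate 0.50, alternative 0.75, type I error 10%, power 75%; stop if successes are at most 5 of 9; fail if at most 10 of 16.

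Probability of early stopping = P(X1 ≤ 5), with X1 ~ Bin(9, p). This gives 382/512 = 0.746 at p = 0.50 and 0.166 at p = 0.75, as stated.

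Probability of declaring feasibility = Σ over x = 6 to 9 of P(X1 = x) × P(X2 ≥ 11 − x), with X2 ~ Bin(7, p).

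At p = 0.50: (84×29 + 36×64 + 9×99 + 1×120) / (512×128) = 5751/65536 = 0.088. At p = 0.75 it is 0.753. The design is sound as stated.

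**2. Drop specimen failures.** Let π be the success rate per enrolled subject and f the fraction of enrolled subjects dropped for an inadequate specimen. None of those dropped could have succeeded, so the rate among those counted is π/(1 − f). Take π = 0.50 and apply the same rule:

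| Assumed f | Counted rate | P(declare feasible) |
|---|---|---|
| 0 | 0.500 | 0.088 |
| 2% | 0.510 | 0.101 |
| 5% | 0.526 | 0.125 |
| 9.1% | 0.550 | 0.168 |
| 12.5% | 0.571 | 0.213 |
| 20% | 0.625 | 0.355 |

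For f = 9.1% the terms are 0.2119×0.3164 + 0.1110×0.6083 + 0.0339×0.8471 + 0.0046×0.9643 = 0.168.

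The protocol gives no specimen-failure rate for this trial, so every f is an assumption. The 9.1% is 20/220, the share not evaluable for any cause, and serves only as a reference size.

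**3. Effect on the reported rate.** A counted rate of 75% corresponds to 0.75 × (1 − 20/220) = 68.2% per enrolled subject at f = 9.1%, and to 0.75 × 0.80 = 60.0% at f = 20%. As an example in one stratum, 11/16 = 68.8% (exact 95% CI 41.3% to 89.0%). Restoring two specimen failures gives 11/18 = 61.1% (35.7% to 82.7%).

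**4. Order of enrollment and biopsy.** Section 2.3 places enrollment before biopsy. Section 9.6 agrees: the laboratories are alerted for tissue collection once the subject meets the criteria. Section 5.2 instead lists the biopsy as screening item 13 and places enrollment after all screening is complete. Under 2.3 an inadequate specimen belongs to an enrolled subject who cannot continue. Under 5.2 it is a screen failure who never enters the trial. Neither route counts it as a feasibility failure.

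**The case against.** The strongest reply is that being barred from continuing is not the same as being removed from the analysis. The endpoint chain starts at enrollment, which reads naturally as a per-enrolled measure, and section 12.3 shows that process failures were foreseen. This stands: bias is a likely consequence of following the text, not something the text prescribes.

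Several stronger readings are tempting, and the documents do not support them:

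- **That the 20 non-evaluable subjects are specimen failures, or that the 16 per stratum are the evaluable ones.** The 200 of 220 is an accrual figure with no reasons attached, and the formal test is a separate count.
- **That a failed subject's slot is refilled.** The protocol contains no such rule.
- **That the earlier feasibility trial shows specimen failures being removed.** Section 1.2 reports 16 enrolled, and then: "2 subjects were deemed ineligible due to tumor type after biopsy". It goes on: "The study endpoint showed that 14/14 patients were feasible to enroll". That is precedent for leaving out subjects found ineligible after biopsy, but the reason was tumor type. All biopsies in that trial are described as adequate.
- **That section 2.3 also removes later failures.** It acts at the pathology check. Failures at sequencing, tumor board, treatment start or cycle 1 are lost only if evaluable means treated.

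One could also argue that under section 5.2 the trial properly estimates feasibility among children with analysable tissue, especially as stored frozen tissue is allowed. That is a legitimate but narrower question than the stated objective, and the plan does not say that it chose it. Finally, the inflated probabilities apply near a true rate of 50%, and nothing in the documents suggests that the rate is that low.

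**Conclusion.** The concern holds as a defect of specification that can bias the primary rate upward. It is not a demonstrated bias. Three features combine: an inadequate specimen becomes ineligibility, the target is set in undefined evaluable subjects who are to be treated, and the feasibility denominator is not stated. The conflict between sections 2.3 and 5.2 adds a second way for the same child to disappear from the result.

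If specimen failures are left out and the true per-enrolled rate is 50%, the chance of declaring feasibility rises from 0.088 to 0.125 at an assumed 5% dropped and to 0.168 at 9.1%. The stated 10% limit is already passed at about 2% (0.101). These figures rest on assumed fractions. How large the effect was in the first cohort cannot be judged from the documents.

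**What to change.** - **Sections 8 and 12.3:** define the primary feasibility denominator as all consented, registered subjects. Count an inadequate specimen and every later missed step in the chain as a failure.
- **Section 2.3:** state that a subject who cannot continue stays in the feasibility analysis.
- **Sections 2.3 and 5.2:** reconcile the order of enrollment and biopsy, so that a consented subject whose specimen proves inadequate appears in the denominator under whichever order is kept.
- **Evaluable:** define the term and reserve it for ORR and PFS.
- **Reporting:** tabulate losses at each step. Give feasibility rates for the first and second cohorts per registered and per evaluable subject, and show subjects found to have the wrong diagnosis separately.

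The cost is wording in these sections and a re-tabulation from enrollment records and the screening log that section 5.2 already requires. No new patients or procedures are needed. The downside is that the stated feasibility rate may fall, and the first-cohort declaration in section 8 would have to be checked against the new denominator.
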